ARES has high sensitivity and specificity¹²³⁻¹²⁵ and better test-retest reliability¹²⁶ than in-lab PSG. We will record 2 nights and calculate respiratory events/total sleep time because of potential night-night variability and score the data through the manufacturer's website with validated automated methods and review by a board certified sleep technician. Although forehead venous pressure distinguished central vs. obstructive respiratory events,¹²³ it is not the gold standard, and we will report only the AHI/RDI. ARES minimizes participant burden and cost, compared with PSG. As in our preliminary study, we will give participants the programmed device and instruction, and they will return it personally or by mail. Drs. [name] and [name] will review scored data and provide patients and referring providers with results/recommendations for follow up.

Randomization/blinding. We will use block randomization to assign participants to groups of 6-8 to assure timely filling of groups and group process. CBT can be provided in groups of 3-12, and groups averaging 5 were used for CBT-I.⁸⁶ As groups complete baseline, we will randomize to treatment assignment with a computer-generated sequence. Recruitment/screening/data collection/data entry personnel will be blinded to group assignment. It is impossible to blind participants, but they will not know the group assignment until the first meeting. Interventionists will be blinded to baseline data and specific hypotheses.

Treatment: CBT-I ("Healthy Sleep" Group: HS). Our manualized protocol includes CBT-I elements (Table 1) in 4 bi-weekly one-hour sessions;^{127,128} a call on alternate weeks; the HS Guide, a workbook with CBT-I components, with sixth grade reading level, print appropriate for older adults, and images reflecting diversity (Appendix); and optional hypnotic tapering. About 80% of hypnotic users selected tapering in our pilot, and we expect hypnotic use to decrease, based on the literature^{81,82} and our experience.²⁰ Four bi-weekly sessions of CBT-I were superior to other frequencies.¹²⁹ The group format was feasible in our pilot, and will enhance social support and learning. Use of a CBT-I trained APRN interventionist is consistent with our²⁹ and other⁹⁴ studies and will promote sustainability due to the greater availability of APRNs than sleep psychologists.

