We will conduct cost-effectiveness analysis (CEA) from a societal perspective where all costs are considered, regardless of who incurs them,^{182,183} document resource use in units, and apply prices to units. Data will be obtained by self-report and validated through the EMR, hospital cost accounting database, and the Medicare fee schedule. Variables will include direct costs for health care resources used [office and emergency department visits, homecare, hospitalizations (and reasons, e.g., HF), cardiac devices, over the counter (OTC) and prescribed medications]. A sub-set of our team, blinded to group assignment, will review hospitalization/ED/office visits and evaluate causes. We will use the electronic pharmacy system to obtain prescription drug utilization and self-report for OTC medications. We will determine costs for prescription and OTC medications with Redbook average wholesale prices and public market prices from drugstore.com. We will include payments to the interventionists and costs of intervention materials. Deaths and causes of death will be ascertained with the EMR. If not found, we will query the National Death Index. Indirect costs will include self-reported time missed from work, travel, and self-management and CBT-I activities. We will measure effectiveness as quality adjusted life years (QALY), estimated from the EQ-6D algorithm from SF-36 data¹⁸⁴ and track research-related costs (monitoring, data collection, personnel costs, and subject payments).

Table 4. Primary Study Variables and Measures: *Baseline, 3 months, 6, 12 months*

Variable	Measure
Sleep/Insomnia	
Global Sleep Quality	Pittsburgh Sleep Quality Index (PSQI); PROMIS Sleep Disturbance Brief Item Bank
Sleep latency (SL), wake after sleep onset (WASO), efficiency (SE), time in bed (TIB), total sleep time (TST)	Subjective: PSQI Objective: Actiwatch2/Wrist Actigraph
Insomnia Severity	Insomnia Severity Index (ISI)
Symptoms	
Excessive Daytime Sleepiness	Epworth Sleepiness Scale (ESS); PROMIS Sleep Impairment Brief Item Bank
Fatigue (total, severity, distress, interference, timing)	Multi-dim Assessment of Fatigue Scale (MAFS)
Depressive Symptoms	PROMIS Depression Short Form 8a
Anxious Symptoms	PROMIS Anxiety Short Form 8a
Pain (severity, location, and interference)	PROMIS Pain intensity-3 item; PROMIS Pain Interference
Dyspnea (total, severity, distress, interference, timing)	Multi-dim Assessment of Dyspnea Scale (MADS)

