We will evaluate treatment enactment/adherence (CBT-I and HF self-management skills use) with bi-weekly calls and review of the HH and HS logs (See treatment section). We will use the Morisky Scale and SCHFI V.6. to assess self-care/self-management (see variables/measures) and evaluate participant flow with CONSORT,¹⁹¹ attendance, and reasons for non-participation, and attrition.

Data Management and Statistical Analysis Plan. We will use REDCap, an NIH-supported electronic data capture application¹⁹² to develop data collection forms. The Yale Program on Aging (POA) hosts Yale's implementation of REDCap (See resources). Data will be entered directly into REDCap with tablets, but we will provide printed forms for all instruments if tablets are not available or fail. Blinded staff will not have access to intervention forms or data. REDCap and study-specific tools and data will be the basis of an administrative system that will support field operations. This blinded tool will enable tracking of recruitment, retention and study progress, scheduling and managing telephone calls, and managing/reporting adverse events. We will develop a separate unblinded database tool for managing intervention schedules and adherence. We will maintain a read-only, de-identified SAS data mart that will be updated daily and will be the basis for conduct-of-study, error-check, and data safety/monitoring reports. Snapshots of the data mart will be used for interim and final analyses.

Data Analysis. We will use Actiware v.6 software (Respironics Minimitter, Inc.) to score actigraph data. Personnel blinded to group assignment will use event markers, light meter and diary recordings to identify “lights on/out” and removal times and to summarize actigraph variables over the 2-week intervals. Use of three methods will minimize problems with missing data (e.g., occlusion of the light meter) for single indicators. Wrist-worn light meters are valid measures of ambient light.¹⁹³

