Data collection will proceed during the follow-up periods as noted above. Participants will be called monthly after the intervention phase until the 12-month follow-up. These calls will elicit any changes in health status and medications, health care utilization (hospitalization, provider visits, emergency department visits, home care use, changes in work status, time associated with the self-management/CBT-I activities). The caller will also elicit concerns about the HH or HS skills, provide problem solving, and remind participants about the next follow-up period. After the 12-month measurement period, participants or their designated family member will be called bi-monthly to elicit changes in health status (hospitalizations, heart transplant, implantation of cardiac devices or artificial hearts, or death) until the end of the study duration. Participants will be informed of the potential duration of follow-up, based on when they were recruited into the study (18-45 months).

Participant will receive \$50 for the sleep apnea screening; and an additional \$250 disbursed over the study milestones. They be able to keep the mini-tablet (estimated value \$60), and the study will provide taxi fare if needed.

2. Characteristics of the study population

The sample will include 200 individuals ≥ 18 years of age with NY Heart Class II-III HF who are cognitively intact by clinical impression, speak/read English, concerned about their sleep for \geq month, and score ≥ 8 on the Insomnia Severity Index,¹⁰⁴ an indicator of ICSD-2 insomnia.¹⁰⁶ Participants will have preserved (LVEF $> 45\%$) or reduced ejection fraction (LVEF $\leq 45\%$). LVEF was not associated with chronic insomnia,⁸ but may contribute. HF patients at the recruitment sites undergo annual echocardiography and with cardiac changes. We will use the most current LVEF. Although sleep continuity is negatively related to age, we will include adults of all ages because of the greater effects of insomnia on fatigue in younger adults.⁸ Participants will receive HF care per the AHA/ACCF guidelines,³⁵ as provided in the study recruitment sites.

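### The monthly follow-up caller both coaches arm-specific skills and collects utilisation data, which contradicts the stated blinding of data collectors; the exposure is mainly the self-reported indirect costs in Aim 3

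*Combined protocol and SAP*

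**What the plan says.** Randomization/blinding (Approach) states: "Recruitment/screening/data collection/data entry personnel will be blinded to group assignment". Telephone follow-up is not excepted. The Data Management and Statistical Analysis Plan section adds: "Blinded staff will not have access to intervention forms or data". It gives the blinded administrative tool the task of "scheduling and managing telephone calls, and managing/reporting adverse events", and provides a separate unblinded database for intervention schedules and adherence.

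Follow-up data collection (Protection of Human Subjects) says: "Participants will be called monthly after the intervention phase until the 12-month follow-up". On content: "These calls will elicit any changes in health status and medications, health care utilization", with "changes in work status, time associated with the self-management/CBT-I activities" among the listed items. It continues: "The caller will also elicit concerns about the HH or HS skills, provide problem solving".

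The retention paragraph of the treatment section describes the monthly calls as scripted and the same in content as the intervention-phase booster calls, apart from meeting reminders. Those boosters ask about skills use and offer review and problem solving.

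For Aim 3, the cost-effectiveness paragraph under the study variables says: "Indirect costs will include self-reported time missed from work, travel, and self-management and CBT-I activities".

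**The concern.** A person who helps a participant with sleep restriction or with fluid management learns which arm the participant is in. So does a person who records time spent on CBT-I. If the same person then asks about missed work, medicines or visits, the depth of questioning can differ by arm without anyone intending it. Such a difference would enter the cost side of Aim 3 directly for any item that has no independent source. The trial would also report that its data collectors were blinded when, for these calls, they could not have been.

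**Working it through.** No stated figure is in dispute, so the main check sets the sections side by side. The arithmetic only gauges materiality.

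**1. Can any caller satisfy the plan?**
- Blinded data collector: contradicts Randomization/blinding and the access limit in Data Management, because skills problem solving and CBT-I time both reveal the arm.
- Interventionist: knows the arm legitimately, but the treatment-fidelity paragraph says interventionists are blinded to outcomes data, and the call collects Aim 3 data.
- Other unblinded staff: avoids the second conflict, but such a person is still collecting data, so the unqualified blinding statement fails.

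No section says who calls, separates the two tasks or sets their order. No reading leaves all the statements true.

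**2. Which items depend on the caller?**

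| Item | Independent source named | Exposure |
|---|---|---|
| Hospital, ED and office visits | EMR and hospital cost accounting; blinded review of causes; record review in each study period | Small: events outside accessible records |
| Prescriptions | Electronic pharmacy system | Small |
| Over-the-counter medicines | Self-report in the cost paragraph; interview and EMR, cross-validated, under Clinical and demographic variables | Partial: EMR capture may be incomplete |
| Missed work, travel, activity time | None specific to the item | Main exposure |

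The cost paragraph opens with a general promise to validate self-report against the EMR, the cost accounting database and the Medicare fee schedule. None of these is an obvious source for the last row. Travel is not named among the call items, so its collection there is an inference.

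**3. How much could it matter?** Inputs from Sample Size: cost difference 500 dollars, SD 2,000 dollars, 100 per group, QALY difference 0.33 in magnitude (printed with a negative sign), threshold 50,000 dollars per QALY. The documents give no size for a reporting bias; 100-200 dollars per person is an assumption.

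- SE of the cost difference = 2,000 × √(2/100) = 283 dollars.
- Bias in SE units: 100/283 = 0.35; 200/283 = 0.71.
- Bias against the planned difference: 100/500 = 20%; 200/500 = 40%.
- Two-sided type I error of a cost-only comparison with no true difference, Φ(b/SE − 1.96) + Φ(−b/SE − 1.96): 6.4% for 100 dollars; 10.9% for 200 dollars.
- Planned net benefit: 0.33 × 50,000 = 16,500, less 500 = 16,000 dollars (17,000 if CBT-I is taken to save 500).
- Bias against net benefit: 100/16,000 = 0.6%; 200/16,000 = 1.3%. On 17,000 it is 0.6% and 1.2%.

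The last figures rest on the large planned QALY difference. If it were one tenth of that (assumption), net benefit would be 0.033 × 50,000 − 500 = 1,150 dollars, and the same bias would be 9-17% of it.

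The stated 89.7% power for Aim 3 cannot be reproduced because no SD for QALYs is given. Nothing here depends on it.

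**The case against.** The other side has a good case on reach. The calls are scripted, which limits free probing, although the scripted content described in the treatment section is skills content and utilisation questions are not mentioned there. Visits and prescriptions have record sources that work whatever the caller asks. Primary outcomes come from questionnaires and from actigraphy scored by blinded personnel. Participants know their arm, so some reporting bias would remain with a perfectly blinded caller. Aim 3 is judged by the ICER and acceptability curve, not by a test of the cost difference alone. All of this stands, and it narrows the point without removing the contradiction.

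A reader might infer more than the documents support:
- *Most utilisation data are compromised.* Record review runs alongside interviews, so recorded events are found regardless.
- *Over-the-counter use has no check.* Clinical and demographic variables provides for EMR validation of it.
- *Event-free survival is compromised.* It is exploratory, with EMR confirmation, blinded review of cause and recourse to the National Death Index. The bi-monthly calls after month 12 have no skills content described. Only events outside the accessible records are exposed.
- *Walk-test or vigilance assessors become unblinded.* No section says that callers run those visits.

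**Conclusion.** The contradiction is certain: for the monthly calls up to month 12, the stated blinding of data collectors cannot hold as written, whoever makes the call. The likely consequence is limited. It falls mainly on self-reported indirect costs, with a smaller exposure for over-the-counter medicines and for events outside accessible records. No primary outcome is affected. On an assumed 100-200 dollars per person, the cost comparison taken alone would shift noticeably (0.35-0.7 SE), while the planned net benefit would move by about 0.6-1.3%. A reader might conclude that the Aim 3 result is unsafe; on the plan's own inputs, where QALYs dominate net benefit, that does not follow. Direction and true size of any bias are unknown. The change is worth making because it is cheap and because the trial should not report a blinding that it lacks.

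**What to change.** Separate the two tasks.

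1. Take utilisation and work items out of the skills call. Either participants enter them in a REDCap form on the study tablet, with a paper option, or blinded staff use an arm-neutral script before, and apart from, any skills content.
2. Have time on CBT-I or self-management activities self-entered, or held in the unblinded database. Blinded staff should not ask for it or see it, because the item reveals the arm.
3. Leave skills problem solving to unblinded staff, schedule those contacts in the unblinded tool, and state who makes each call. An interventionist in this role should not see the utilisation answers.

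If the call stays combined, limit the statement in Randomization/blinding so that it excludes these calls, and report call-collected utilisation and indirect costs as unblinded self-report.

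The cost is a revised script and form, plus one short self-entered form or a second brief contact per month. The effect on staffing depends on who makes the calls now, which the documents do not say. Separation removes bias driven by the caller; reporting bias from unblinded participants remains and should be acknowledged.
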